1.4.6 Risk of Loss of Confidentiality

There is always a potential for the loss of confidentiality. This risk will be minimized by keeping all study data stored and secured. Electronic data will be password protected. Private information will only be given out as listed in the Health Insurance Portability and Accountability Act (HIPAA) form.

1.4.7 Unexpected Risk and Discomforts

There may be risks in this study that are not yet known, or that happens rarely when subjects take these study drugs. Subjects will be told of any new information that could affect their safety during study participation.

1.4.8 Potential Benefits

All patients with HIV-1 infection should receive effective antiretroviral therapy. Selection of drugs for HIV-1 patients coinfecte with HBV should take into consideration the regimen's anti-HBV activity to prevent potentially life-threatening hepatitis flares. B/F/TAF FDC regimen has the potential to offer HIV-HBV infected patients a simple, once daily regimen containing drug components that provides a high barrier to resistance against both HIV-1 and HBV. B/F/TAF does not require a boosting agent, and offers an effective and safe alternative to other regimens, without need for HLA testing or close monitoring of renal or bone toxicities. In addition, patient participation in this study will contribute to the body of knowledge about treatment for HIV-HBV coinfection.

2 OBJECTIVES

2.1 Primary Objective

- To evaluate the efficacy of fixed dosed combination (FDC) bictegravir/emtricitabine/tenofovir alafenamide (B/F/TAF) in adult subjects coinfected with HIV-1 and HBV, as determined by HIV-1 RNA <50 copies/mL at Week 24 by US FDA Snapshot Algorithm and/or HBV DNA <29 IU/mL at Week 24 by missing = failure method.

2.2 Secondary Objectives

- Evaluate the safety and tolerability of FDC B/F/TAF in HIV-HBV coinfected subjects.
- Evaluate the efficacy of FDC B/F/TAF in adult subjects coinfected with HIV-1 and HBV, as determined by HIV-1 RNA <50 copies/mL at Week 48 by FDA Snapshot Algorithm.
- Evaluate the efficacy of FDC B/F/TAF in adult subjects coinfected with HIV-1 and HBV, as determined by HBV DNA <29 IU/mL at Week 48 by missing = failure method.
- Evaluate the efficacy of FDC B/F/TAF in adult subjects coinfected with HIV-1 and HBV, as determined by improvement in CD4 count, ALT normalization, HBeAg loss, HBsAg loss, and improvement in Fibroscan test scores from baseline to Week 24 and Week 48.

2.3 Exploratory Objectives

- Evaluate changes in quantitative HBsAg levels during treatment with FDC B/F/TAF.
- Evaluate any changes in immune activation markers (plasma hsCRP, IL-6, TNF- α , and D-dimer and cellular HLA-DR+CD38+ CD4 and CD8 T lymphocytes) during treatment with FDC B/F/TAF.

2.4 Primary Endpoints

- Proportion of subjects with HIV-1 RNA <50 copies/mL at Week 24 by FDA Snapshot Algorithm.
- Proportion of subjects with HBV DNA <29 IU/mL at Week 24 by missing = failure method.

2.5 Secondary Endpoints

- Proportion of subjects with HIV-1 RNA <50 copies/mL at Week 48 by FDA Snapshot Algorithm.
- Proportion of subjects with HBV DNA <29 IU/mL at Week 48 by missing = failure method.
- Assessment of the safety and tolerability of the FDC B/F/TAF in HIV-HBV coinfected subjects as measured by the proportion of subjects who discontinue study medications due to AE.
- Change from baseline in CD4 cell count and percentage at Week 24 and at 48.

- Proportion of subjects with normalized ALT at Week 24 and Week 48.
- Proportion of subjects with HBV e antigen (HBeAg) loss and seroconversion to anti-HBe at Week 24 and Week 48.
- Proportion of subjects with HBV surface antigen (HBsAg) loss and seroconversion to anti-HBs at Week 24 and Week 48.
- Change from baseline in Fibroscan test score at Week 24 and Week 48.

2.6 Exploratory Endpoints

[figure not shown]
- Change from baseline in quantitative HBsAg at Week 24 and Week 48.
- Assessment of changes in immune activation markers (plasma hsCRP, IL-6, TNF- α , and D-dimer and cellular HLA-DR+CD38+ CD4 and CD8 T lymphocytes) during treatment with FDC B/F/TAF.

3 INVESTIGATIONAL PLAN

3.1 Summary of Study Design

This is a multicenter, open-label phase 4 study to evaluate the efficacy, safety, and tolerability of treatment with fixed dosed combination bictegravir/emtricitabine/tenofovir alafenamide in adults with HIV-1 and HBV coinfection who are currently on a stable antiretroviral regimen for at least 3 months. Two sites are planned to participate: Institute of Human Virology (IHV), University of Maryland, Baltimore, MD and Philadelphia Department of Health (DOH) Clinic. Subjects who provide written informed consent and meet all eligibility criteria will receive fixed dose combination of Bictegravir 50 mg/Emtricitabine 200 mg/tenofovir alafenamide 25 mg (B/F/TAF) administered orally one pill once daily, without regard to food. Study treatment duration for enrolled subjects will be 48 weeks. Safety evaluations will consist of adverse event, physical examination (including vital signs), and clinical laboratory data. Efficacy will be evaluated by HIV RNA and HBV DNA levels.

Figure 3-1. Study Schema

3.2 Study Procedures

See also Schedule of Activities ([Appendix A](#)).

3.2.1 Pretreatment Assessments

3.2.1.1 Screening Assessments (Day -90 to Day -3)

The following screening assessments must be done to determine subject eligibility. Written consent will be obtained before conducting any study procedures.

- Screen for inclusion/exclusion (see [Section 5](#)).
- Medical History.
- Complete physical examination, including weight, height, and vital signs (blood pressure, respiratory rate, heart rate, and temperature).
- Collect concomitant medication information.
- 12-lead electrocardiogram (ECG).
- Plasma HIV-1 RNA.
- Plasma HBV DNA.
- Quantitative HBsAg level.
- CD4 cell count.
- HBV profile [HBsAg, HBeAg, anti-HBs, anti-HBe, and anti-HBc both IgM and total].
- HCV serology.
- HDV serology.
- Complete blood count [hematocrit, hematocrit, erythrocyte count (RBC), white blood cell count (WBC), percentage and absolute WBC differential counts, platelet count].
- Comprehensive metabolic panel [glucose, blood urea nitrogen, creatinine, sodium, potassium, chloride, total carbon dioxide, calcium, total protein, albumin, total globulin, total bilirubin, alkaline phosphatase, alanine aminotransferase, aspartate aminotransferase].
- Coagulation tests [activated partial thromboplastin time (PTT), prothrombin time (PT), international normalized ratio (INR)].
- Urinalysis.
- Serum pregnancy test for women of childbearing potential (defined as a woman who is physiologically capable of becoming pregnant).

With the exception of the serum pregnancy test, outside clinical laboratory tests may be used for screening if it was done within 90 days of screening.

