1 INTRODUCTION

1.1 Background & Scientific Rationale

Human immunodeficiency virus-1 (HIV-1) infection is a life-threatening and serious disease that is of global public health importance. More than 37 million people worldwide are living with HIV-1 infection. Of these HIV-1 infected populations, about 5-20% are also coinfected with the hepatitis B virus (HBV) ([Singh K, et al. 2017](#)). In the United States (U.S.), about 10% of people with HIV are coinfected with HBV, and about 20% of all new HBV infections are among gay and bisexual men ([CDC Fact Sheet 2017](#)). HIV-HBV coinfection has been associated with a higher risk of morbidity and mortality, especially with regard to accelerated liver disease progression leading to hepatic failure, need for liver transplantation, and death ([Colin JF, et al. 1999; Thio CL 2002](#)). In addition, HBV coinfection accelerates immunologic and clinical progression of HIV infection as well as increases the risk of hepatotoxicity when combination antiretroviral therapy (ART) are used ([Sun HY et al. 2014](#)). Nevertheless, the availability of HBV-active ART regimens has significantly improved the outcome of the HIV-HBV coinfected population, leading to longer life expectancies and lower rates of morbidities.

The University of Maryland Medical System has multiple clinical practices that care for patients living with HIV-1 and chronic HBV. Close to four thousand patients infected with HIV-1 are under its care. The estimated prevalence rate of HIV-HBV coinfection in these clinical practices are between 2-3%. The HIV/HBV target population is predominantly Black or of African American heritage (89%) followed by White (9.6%), and close to 80% are males. Approximately 87% are already on tenofovir (either TDF or TAF) based regimen as part of their backbone NRTI. In addition, majority of these coinfected patients are on integrase inhibitor (63.8%), though some are still on NNRTIs (14.5%) and others on various protease inhibitors (21.7%). Of those on integrase inhibitors, two-thirds are on dolutegravir (65.9%), while the rest are on either elvitegravir (27.3%) or raltegravir (6.8%).

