9.2.3 Analysis of the Secondary Endpoints

The secondary endpoints include:

- The proportion of subjects with HIV-1 RNA < 50 copies/mL at Week 48 as defined by the US FDA Snapshot Algorithm.
- The proportion of subjects with plasma HBV DNA < 29 IU/mL at Week 48 using the missing = failure method.
- Change from baseline in CD4 cell count and percentage at Week 24 and at 48.
- Proportion of subjects with normalized ALT at Week 24 and Week 48.
- Proportion of subjects with HBV e antigen (HBeAg) loss and seroconversion to anti-HBe at Week 24 and Week 48.
- Proportion of subjects with HBV surface antigen (HBsAg) loss and seroconversion to anti-HBs at Week 24 and Week 48.
- Change from baseline in Fibroscan test score at Week 24 and Week 48.

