APPENDIX A. SCHEDULE OF ACTIVITIES

Study Procedures	Screening (D-90 to -3)	Day 1	Study Week					
			4	8	12	24	36	48 ^g
Administrative Procedures								
Informed Consent	X							
Inclusion/Exclusion Criteria	X	X						
Complete Medical History	X							
Interval Medical History		X	X	X	X	X	X	X
Administer 1st Dose of Study Drug		X						
Study Drug and Diary Dispensation		X	X	X	X	X	X	
Study Drug Accountability			X	X	X	X	X	X
Clinical Procedures/Assessments								
Complete Physical Exam	X	X						X
Targeted Physical Exam, if needed			X	X	X	X	X	
Concomitant medication	X	X	X	X	X	X	X	X
Adverse event		X	X	X	X	X	X	X
Height	X							
Vital Signs (T, P, R, BP) and Wt	X	X	X	X	X	X	X	X
12-lead ECG	X							
Clinical Laboratory Tests								
Plasma HIV-1 RNA	X ^a	X	X	X	X	X	X	X
Plasma HBV DNA	X ^a	X	X	X	X	X	X	X
Quantitative HBsAg level	X ^a	X	X	X	X	X	X	X
CD4 Cell Count	X ^a	X			X	X	X	X
HBsAg/HBcAb/HBsAb/HBeAg/HBeAb	X ^a					X		X
HIV-1 Genotype/Phenotype ^b		X						X
HBV Resistance Assay ^c		X						X
HBV Genotype ^c		X						
HCV serology	X ^a							
HDV serology	X ^a							
CBC	X ^a	X	X	X	X	X	X	X
CMP	X ^a	X	X	X	X	X	X	X
Coagulation Tests (PT/PTT)	X ^a							X
Fibroscan (IHV only)		X ^e				X ^f		X ^f
Urinalysis	X ^a							
Urine pregnancy test (if WOCP ^d)		X	X	X	X	X	X	X
Serum pregnancy test (if WOCP ^d)	X							
Research Laboratory Tests								
PAXgene RNA Assay		X			X	X	X	X
PAXgene DNA Assay		X						
PBMC Storage		X	X	X	X	X	X	X
Plasma Storage		X	X	X	X	X	X	X
Serum Storage		X	X	X	X	X	X	X

[figure not shown]
Legend:

- ^a May use outside labs if within 90 days.
- ^b If HIV-1 RNA is ≥ 500 copies/mL
- ^c If HBV DNA is ≥ 500 IU/mL
- ^d Woman of childbearing potential
- ^e Fibroscan at Baseline (Day 1) may be conducted within 30 days prior to Day 1 Visit.
- ^f Fibroscan at Week 24 and Week 48, may be conducted 2 weeks before or after the Study Visit.
- ^g Week 48 (End of Study) Visit procedures will be used for Early Termination/Subject Withdrawal Visits.

[figure not shown]

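### HBeAg, anti-HBe and anti-HBs have no Day 1 value, so changes on the previous regimen can be counted as responses to B/F/TAF

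*Combined protocol and SAP*

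**What the plan says.** Sections 2.5 and 9.2.3 list as a secondary endpoint the "Proportion of subjects with HBV e antigen (HBeAg) loss and seroconversion to anti-HBe at Week 24 and Week 48", with a parallel endpoint for HBsAg and anti-HBs. Neither section says which sample is the baseline or who belongs in the denominator.

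The qualitative serology row in Appendix A, "HBsAg/HBcAb/HBsAb/HBeAg/HBeAb", is marked at screening, Week 24 and Week 48. Day 1 is not marked, and the Day 1 list in section 3.2.2 does not include the panel.

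Screening runs from Day -90 to Day -3. Section 3.2.1.1 states that, apart from the pregnancy test, "outside clinical laboratory tests may be used for screening if it was done within 90 days of screening". Footnote a of Appendix A, attached to the same row, says only "May use outside labs if within 90 days" and gives no date to count from.

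Other measures are handled more tightly. HIV-1 RNA, HBV DNA, CD4, the metabolic panel (hence ALT) and quantitative HBsAg are redrawn on Day 1 before dosing, and the baseline FibroScan must fall within 30 days of Day 1. Section 9.2.8 equates baseline with Day 1, but only for the exploratory markers. Section 9.2.7 plans a subgroup by baseline HBeAg status without saying which sample defines it. Serum and plasma are banked on Day 1, with no serology planned on them.

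**The concern.** The study has one arm (section 6.2), and its subjects switch from another regimen. Section 1.1 says of the target population: "Approximately 87% are already on tenofovir (either TDF or TAF) based regimen". Section 1.1.1 itself reports antigen loss on long-term tenofovir, so these events can occur before the switch.

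A subject who was HBeAg-positive at an old screening test, lost HBeAg on the previous regimen and then started B/F/TAF would be HBeAg-negative at Week 24. With screening as the only earlier value, that subject looks the same as one who lost HBeAg on study drug, and no control arm offsets the error. Because only three months on an unchanged regimen are required for entry, a 180-day-old result could even predate the regimen being replaced.

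At stake is the interpretation of rare secondary events, where a single misdated case changes the reported rate noticeably, and the make-up of the HBeAg subgroup.

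**Working it through.** **The plan's own figures.** The plan states no number for these endpoints. Its one design figure, 84% power for the Week 24 HIV-1 endpoint, reproduces closely: with N = 60 and a null of 0.773, rejection at 53 or more successes has exact alpha 0.0237 and power 83.1% at 0.910. Serology does not enter that calculation.

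**Inputs.**
- Screening window: up to 90 days before Day 1 (section 3.2.1.1).
- Look-back for outside results: 90 days before screening (section 3.2.1.1), or 90 days from an unstated date (Appendix A, footnote a).
- Treatment time: T = 24 × 7 = 168 days and 48 × 7 = 336 days.
- Illustrative 48-week seroconversion rates from the cited switch study (section 1.1.1): 3.9% of HBeAg-positive and 2.9% of HBsAg-positive subjects.

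**Age of the pre-dose result.** On the section 3.2.1.1 wording the maximum is 90 + 90 = 180 days. Counting footnote a from Day 1 gives 90 days. A study sample drawn at Day -90 is also 90 days old, so that gap does not depend on outside results at all. The shortest gap is 3 days, for a sample drawn at Day -3.

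**Pre-dose share of the interval between the two serology results,** L/(L + T):

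| Gap L | Week 24 (T = 168) | Week 48 (T = 336) |
|---|---|---|
| 3 days | 3/171 = 1.8% | 3/339 = 0.9% |
| 90 days | 90/258 = 34.9% | 90/426 = 21.1% |
| 180 days | 180/348 = 51.7% | 180/516 = 34.9% |

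Across the Week 24 window (Day 140 to 196), the 180-day share runs from 180/376 = 48% to 180/320 = 56%.

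**Events.** Assume a constant hazard h = -ln(1 - r)/336, the same on both regimens, and every result 180 days old. The pre-dose probability is 1 - exp(-180h), the apparent rate is 1 - exp(-h(180 + T)), and the true on-treatment rate is 1 - exp(-hT).

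| r | Pre-dose | Week 24 apparent / true | Week 48 apparent / true | Pre-dose events if all 60 are at risk |
|---|---|---|---|---|
| 3.9% | 2.11% | 4.0% / 2.0% | 5.9% / 3.9% | 60 × 0.0211 = 1.27 |
| 2.9% | 1.56% | 3.0% / 1.5% | 4.4% / 2.9% | 60 × 0.0156 = 0.94 |

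With a 90-day gap the last column falls to 0.64 and 0.47.

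**The case against.** A reader might infer that HBsAg loss has the same defect. It does not. Quantitative HBsAg is drawn on Day 1 before dosing and at every later visit, so HBsAg loss on the old regimen would be visible there. What is missing is a statement that this value is the baseline. Only the antibody part of HBsAg seroconversion, anti-HBs, lacks a Day 1 test.

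A reader might also infer that the plan credits earlier events to B/F/TAF. It gives no baseline rule for these endpoints, so it permits the misattribution without prescribing it. Stored Day 1 serum would allow a later check. Even so, for HBeAg, anti-HBe and anti-HBs an analyst following the schedule has only the screening value to use.

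The size is open to challenge too. The 180-day gap needs the earliest screening day and the oldest acceptable outside result together. The documents give no actual gaps. HBeAg positivity is not an entry requirement and its prevalence is not given, so far fewer than 60 subjects may be at risk. These are secondary endpoints with no stated hypothesis test. All of this stands and limits the importance of the point. It does not supply the missing Day 1 value.

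**Conclusion.** The point holds for HBeAg loss, HBeAg seroconversion, the appearance of anti-HBs and the HBeAg subgroup. Their only planned pre-dose value may be up to 180 days old on one wording and up to 90 days on another reading, and the two places need to be reconciled.

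It would be tempting to say that half of the Week 24 responses belong to the previous regimen. The documents do not support that. The 52% is a ceiling, reached only if every result is 180 days old and the event rate is constant and equal on both regimens. In absolute terms about one misdated event at most is expected at the cited rates (0.94 to 1.27 with all 60 at risk), and fewer with realistic gaps and denominators. Those rates are for seroconversion. The documents give no rate for HBeAg loss alone in that study, and the expected count would move roughly in proportion to the rate.

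The primary endpoints and the power calculation are unaffected. The change is still worth making, because it is cheap and the few events involved are what readers will look at.

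**What to change.** 1. Add HBeAg, anti-HBe and anti-HBs to the pre-dose Day 1 blood draw in section 3.2.2 and Appendix A.
2. For subjects already enrolled, run the three tests on stored Day 1 serum for everyone with a sample and consent. Testing only subjects with events would classify the HBeAg subgroup by outcome and leave already-negative subjects in the denominator.
3. Where no Day 1 sample exists, use the last pre-dose value. Report how many subjects this affects and the age of their results.
4. State in section 9.2.3 that baseline is Day 1, with quantitative HBsAg defining HBsAg status.
5. Base the numerator, the denominator (antigen-positive at baseline, and also antibody-negative for seroconversion) and the section 9.2.7 HBeAg subgroup on that value.
6. Reconcile footnote a with section 3.2.1.1 by giving it a reference date.

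With a Day 1 result the gap falls to 0 days and the pre-dose share to 0%. The cost is one extra serology panel per subject on blood already drawn, with no new visit. Reported loss or seroconversion rates may be slightly lower. Stored serum will not be available for everyone, because section 10.4 lets participants withdraw consent for optional stored specimens, which are then destroyed. The samples were banked for later research, so their use for an endpoint should be checked against the consent.

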3.2.2 Day 1 Assessments

Screening tests must be available before the subject is eligible for study participation. Once screening is completed and the subject meets all eligibility criteria, the subject will obtain baseline evaluations. Study drug administration may occur after completion of all baseline procedures.

Before Study Drug Administration:

- Review eligibility criteria (see [Section 5](#)) and confirm eligibility of subject.
- Obtain interval medical history.
- Conduct complete physical examination, including weight and vital signs [blood pressure (BP), respiratory rate (R), heart rate (HR), and temperature (T)].
- Collect concomitant medication information.
- Plasma HIV-1 RNA
- Plasma HBV DNA.
- Quantitative HBsAg level.
- CD4 cell count.
- HIV-1 genotype/phenotype, if HIV-1 RNA is ≥ 500 copies/mL.
- HBV genotype and resistance assay, if HBV DNA is ≥ 500 IU/mL.
- Complete blood count.
- Comprehensive metabolic panel.
- Urine pregnancy test for women of childbearing potential.
- FibroScan test (IHV only) – this test may be conducted within 30 days prior to or on the Day 1 Visit.
- Blood for PAXgene DNA and RNA analysis.
- Blood for storage of plasma, serum, and peripheral blood mononuclear cells (PBMC) for future research purposes.

Study Drug Administration (and Post-Study Drug Assessments):

- Administer first dose of B/F/TAF.
- Dispense study drug supply (remainder of 60-day supply).
- Reinforce study drug instruction: subjects are to take one (1) tablet of B/F/TAF once daily upon awakening with at least 8 oz. of plain water, and without regards to food.
- Dispense Study Drug Diary.
- Collect adverse event information.
- Collect concomitant medication information.
- Instruct subject to bring all study drugs and bottles to each future study visits.

3.2.3 Treatment Assessments

3.2.3.1 Week 4 and 8 Visits (\pm 7 days)

- Obtain interval medical history.
- Conduct targeted physical examination (if needed), including weight and vital signs [BP, R, HR, T].
- Collect concomitant medication information.
- Collect adverse event information.
- Evaluate Patient Diary and number of used and unused tablets.
- Plasma HIV-1 RNA.
- Plasma HBV DNA.
- Quantitative HBsAg level.
- Complete blood count.
- Comprehensive metabolic panel.
- Urine pregnancy test for women of childbearing potential.
- Blood for storage of plasma, serum, and PBMCs.
- Dispense study drug supply (30-day supply for Week 4; 60-day supply for Week 8).
- Reinforce study drug instruction: subjects are to take one (1) tablet of B/F/TAF once daily upon awakening with at least 8 oz. of plain water, and without regards to food.
- Instruct subject to bring all study drugs and bottles to each future study visits.

3.2.3.2 Week 12, 24, and 36 Visits (\pm 2 weeks for Week 12 and Week 36; \pm 4 weeks for Week 24)

- Obtain interval medical history.
- Conduct targeted physical examination (if needed), including weight and vital signs [BP, R, HR, T].
- Collect concomitant medication information.
- Collect adverse event information.
- Evaluate Patient Diary and number of used and unused tablets.
- Plasma HIV-1 RNA.
- Plasma HBV DNA.
- Quantitative HBsAg level.
- CD4 cell count.
- Complete blood count.
- Comprehensive metabolic panel.
- Urine pregnancy test for women of childbearing potential.
- Blood for PAXgene RNA analysis.
- Blood for storage of plasma, serum, and PBMCs.

- Dispense study drug supply (90-day supply).
- Reinforce study drug instruction: subjects are to take one (1) tablet of B/F/TAF once daily upon awakening with at least 8 oz. of plain water, and without regards to food.
- Instruct subject to bring all study drugs and bottles to each future study visits.

Additional Week 24 assessments:

- HBV profile.
- FibroScan test (IHV only). This test may be done during the Week 24 visit, or within 2 weeks (before or after) the scheduled Week 24 visit.

3.2.3.3 Week 48 Visit (\pm 4 weeks): End-of-Study Assessments

This describes the end-of-study assessments for all subjects including those who discontinue study prematurely.

- Obtain interval medical history.
- Conduct complete physical examination, including weight and vital signs [BP, R, HR, T].
- Collect concomitant medication information.
- Collect adverse event information.
- Evaluate Patient Diary and number of used and unused tablets.
- Plasma HIV-1 RNA.
- Plasma HBV DNA.
- Quantitative HBsAg level.
- CD4 cell count.
- HIV-1 genotype/phenotype, if HIV-1 RNA is \geq 500 copies/mL.
- HBV genotype and resistance assay, if HBV DNA is \geq 500 IU/mL.
- HBV profile.
- Complete blood count.
- Comprehensive metabolic panel.
- Coagulation tests.
- Urine pregnancy test for women of childbearing potential.
- FibroScan test (IHV only). This test may be done during the Visit, or within 2 weeks (before or after) the scheduled Week 48 visit.
- Blood for PAXgene RNA analysis.
- Blood for storage of plasma, serum, and PBMCs.

